5.3 Statistical Methods and Analyses to be Performed

The proportion of FNAIT laboratory test subgroups among Baseline Screened Population or Alloimmunization Follow-up Population will be presented with their respective 80%, 90% and 95% confidence intervals.

5.3.1 Discussion of Analytical Approaches

The statistical analyses will be performed in accordance with Good Pharmacovigilance Practice (GPP) guideline / International Conference on Harmonisation (ICH) E9 guideline and will be based on the pooled data from the individual study sites, unless otherwise stated. The Statistical analysis will be performed by Parexel and reviewed by Rallybio.

5.3.2 Analysis of the Baseline Screened Population

The proportion of participants at higher risk for HPA-1a alloimmunization will be determined from the Baseline Screened Population and summarized descriptively.

The proportion will be calculated as (the number of participants determined at baseline to be at higher risk for HPA-1a alloimmunization) / (all enrolled participants who meet Inclusion/Exclusion criteria and who have complete final FNAIT screening tests results, as defined in Section 3.2.1). Listing for participants who are HPA-1b/b, HLA-DRB3*01:01 positive and HPA-1a alloantibody negative at baseline (Baseline Screened Population) and listing for Participants who are HPA-1b/b, HLA-DRB3*01:01 positive and HPA-1a alloantibody positive at baseline (Baseline Screened Population) are provided for publication purposes.

In addition to the above, maternal demographics, obstetric history and other baseline characteristics will be analyzed, including:

- Age at screening and BMI
- Obstetric History will be summarized by 1 or more prior pregnancies, 2 or more prior pregnancies, 3 or more prior pregnancies, and 4 or more prior pregnancies (including history of prior pregnancies with mode of delivery, pregnancy outcomes)
- Proportion of participants by region, by self-characterized classification of race and ethnicity or by race (White vs. Others), and by OMB classification of race and ethnicity
 - With attention to region (Europe vs. North America), first vs. second or later pregnancy, self-characterized classification of race and ethnicity or by race (White vs. Others), and OMB classification of race and ethnicity
 - With attention to region (Europe vs. North America) and then further broken down by OMB classification of race and ethnicity
- Proportion of participants who are HPA-1b/b
 - With attention to region (Europe vs. North America), first vs. second or later pregnancy, self-characterized classification of race and ethnicity or by race (White vs. Others), and OMB classification of race and ethnicity
- Proportion of participants who are HPA-1b/b and HLA-DRB3*01:01 positive
 - With attention to region (Europe vs. North America), first vs. second or later pregnancy, self-characterized classification of race and ethnicity or by race (White vs. Others), and OMB classification of race and ethnicity
- Proportion of participants who are HPA-1b/b, HLA-DRB3*01:01 positive and HPA-1a alloantibody negative

- With attention to region (Europe vs. North America), first vs. second or later pregnancy, self-characterized classification of race and ethnicity or by race (White vs. Others), and OMB classification of race and ethnicity
- Proportions of participants who are HPA-1b/b, HLA-DRB3*0101 positive, HPA-1a alloantibody negative, and are bearing an HPA-1a antigen positive fetus
 - With attention to region (Europe vs. North America), first vs. second or later pregnancy, self-characterized classification of race and ethnicity or by race (White vs. Others), and OMB classification of race and ethnicity
- Proportion of participants who are HPA-1b/b, HLA-DRB3*0101 and HPA-1a alloantibody positive at baseline
 - With attention to region (Europe vs. North America), first vs. second or later pregnancy, self-characterized classification race and ethnicity or by race (White vs. Others), and OMB classification of race and ethnicity
- Proportion of participants by region by pre-natal FNAIT laboratory testing results
- Proportion of participants by pregnancy history by pre-natal FNAIT laboratory testing results
- Proportion of participants by self-characterized classification of race and ethnicity by pre-natal FNAIT laboratory testing results
- Proportion of participants by race (White vs. Others) by pre-natal FNAIT laboratory testing results
- Proportion of participants by OMB classification of race and ethnicity by pre-natal FNAIT laboratory testing results
- Summary of pregnancy history (with prior pregnancy vs no pregnancy) by region, race and ethnicity: a column about total number of participants in specific region, race, or ethnicity category in Baseline Screened Population needs to be included, and the proportion of those with prior pregnancy or no pregnancy is the number of specific region, race, or ethnicity participants with prior pregnancy or no pregnancy divided by the total number of specific region, race, or ethnicity participants
- Summary of prior pregnancies for participants who are HPA-1b/b and HLA-DRB3*01:01 positive and participants who are HPA-1b/b, HLA-DRB3*01:01 positive and HPA-1a alloantibody negative by region (Total included)
- Summary of the median number of prior pregnancies in Baseline Screened Population broken down by Region, OMB race and ethnicity

5.3.3 Analysis of the Alloimmunization Follow-up Population

5.3.3.1 Baseline characteristics

Baseline characteristics include age at screening, BMI, self-characterized classification of race and ethnicity or by race (White vs. Others), OMB classification of race and ethnicity, estimated gestational age, and obstetric history (including history of prior pregnancies with mode of delivery, gestational age of delivery, pregnancy outcome).

5.3.3.2 Occurrence of anti-HPA-1a maternal alloimmunization at Week 10 postpartum

The proportion of participants who HPA-1a alloimmunize among the Alloimmunization Follow-up Population will be summarized descriptively.

The proportion will be calculated as (the number of participants with HPA-1a alloimmunization postpartum) / (the total number of pregnant women identified to be at higher risk for HPA-1a alloimmunization, and who have a Week 10 postpartum HPA-1a alloimmunization test result) and with attention to region (Europe vs. North America), first vs. second or later pregnancy, -self-characterized classification of race and ethnicity or by race (White vs. Others), and OMB classification of race and ethnicity.

A comparison table for the summary of OMB classification of Race and Ethnicity between Baseline Screened Population and Alloimmunization Follow-up Population is needed for publication purposes.

A listing of all participants in the Alloimmunization follow up population will be provided, sorted by those with a positive alloimmunization and those with a negative alloimmunization at week 10 postpartum. In addition, a listing with the same data elements will be provided for those participants at higher risk for HPA-1a alloimmunization for whom a 10 week follow up alloimmunization determination is missing.

Data elements for both listings will include Participant ID, Country, maternal age at screening, race (self-characterized), ethnicity, BMI, pregnancy outcome (live births, premature births, stillbirths, spontaneous abortions, elective abortions), reason for termination for pregnancy, gestational age at birth, obstetric history, any interventions for FNAIT during the pregnancy (e.g. IVIG, or interventions other than IVIG), 10-week postpartum HPA-1a alloimmunization status, neonatal platelet count (where available), and additional neonate outcome.

For the separate listing of those who did not have 10 weeks alloimmunization determination, data elements will be the same with the addition of the reason for no determination will be listed as well (e.g. lost to follow-up, withdrew consent) and “unknown” or column deleted for week 10 postpartum HPA-1a alloimmunization status.

5.3.3.3 Pregnancy outcomes

Pregnancy outcomes include the rate of spontaneous abortion, elective abortion, stillbirth, premature birth, and live births among pregnant women identified to be at higher risk for HPA-1a alloimmunization and who have a Week 10 postpartum HPA-1a alloimmunization test result (Alloimmunization Follow-up Population). Pregnancy outcomes will be further broken down by HPA-1a alloimmunization status at Week 10 postpartum (alloimmunized/not alloimmunized) and with attention to region (Europe vs. North America), first vs. second or later pregnancy, and self-characterized classification of race and ethnicity or by race (White vs. Others), and OMB classification of race and ethnicity. Additional listing about pregnancy outcomes for Alloimmunization Follow-up Population will be provided, and the data elements will include pregnancy outcome, HPA-1a alloimmunization status at Week 10 postpartum, race and ethnicity.

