3 RESEARCH OBJECTIVES AND OUTCOME VARIABLES

Research Objectives	Outcome Variables
Primary	
To inform the frequency of women at higher FNAIT risk among pregnant women of different racial and ethnic characteristics who present for pre-natal care.	The number of participants that are determined to be at higher FNAIT risk compared to the total number of pregnant women assessed for higher FNAIT risk, with attention to self-characterized race and ethnicity.
Secondary	
To inform the frequency of HPA-1a alloimmunization among pregnant women identified at higher FNAIT risk.	Occurrence of anti-HPA-1a maternal alloimmunization at Week 10 postpartum ^a
To inform the frequency of pregnancy outcomes among pregnant women identified at higher FNAIT risk.	
 • Rate of spontaneous abortion, defined as non-deliberate fetal death which occurs prior to 19 weeks of gestation • Rate of elective abortion, defined as deliberate termination of pregnancy at any time in gestation • Rate of stillbirth, defined as non-deliberate fetal death anytime in gestation on or after 19 weeks of gestation • Rate of premature birth, defined as live birth prior to 37 completed weeks of gestation • Rate of live births (≥ 37 completed weeks of gestation)
To inform the frequency, where data are available, of neonatal thrombocytopenia in infants born to women who have alloimmunized, as determined by detectable anti-HPA-1a antibody at Week 10 postpartum. ^a	Neonatal thrombocytopenia and severe neonatal thrombocytopenia, as determined by a platelet count $< 150 \times 10^9/L$ and $< 50 \times 10^9/L$ respectively, within 72 hours of birth, where data are available

^a For pregnancies that do not result in a live birth, the assessment of alloimmunization will be at 10 weeks from the date of the pregnancy-terminating event (ie, abortion [spontaneous/elective] or stillbirth).

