4.2.3 Visit Assessments for Pregnancy Outcomes that are Not Live Births

For pregnancies that do not result in a live birth, the assessment of alloimmunization will be at 10 weeks from the date of the pregnancy-terminating event (ie, abortion [spontaneous/elective] or stillbirth).

- A blood sample will be collected for the assessment of maternal alloimmunization (refer to the study Laboratory Manual for details), as determined by the presence of detectable anti-HPA-1a antibodies.
- Pregnancy outcome: spontaneous abortion, elective abortion, stillbirth, including the date (based on medical records)
- Interventions used: eg, IVIG, steroids

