2 RESEARCH OBJECTIVES AND OUTCOME VARIABLES

Table 1 Research Objectives and Outcome Variables

Research Objectives	Outcome Variables
Primary	
To inform the frequency of women at higher risk for HPA-1a alloimmunization among pregnant women of different racial and ethnic characteristics who present for pre-natal care.	The number of participants that are determined to be at higher risk for HPA-1a alloimmunization compared to the total number of pregnant women assessed for higher risk for HPA-1a alloimmunization, with attention to self-characterized race and ethnicity.
Secondary	
To inform the frequency of HPA-1a alloimmunization postpartum among pregnant women identified to be at higher risk for HPA-1a alloimmunization.	Occurrence of anti-HPA-1a maternal alloimmunization at Week 10 postpartum. *
To inform the frequency of specific pregnancy outcomes among pregnant women identified to be at higher risk for HPA-1a alloimmunization.	
 • Rate of spontaneous abortion, defined as non-deliberate fetal death which occurs prior to 19 weeks of gestation. • Rate of elective abortion, defined as deliberate termination of pregnancy at any time in gestation. • Rate of stillbirth, defined as non-deliberate fetal death anytime in gestation on or after 19 weeks of gestation. • Rate of premature birth, defined as live birth prior to 37 completed weeks of gestation. • Rate of live births (≥ 37 completed weeks of gestation).

To inform the frequency, where data are available, of neonatal thrombocytopenia in infants born to women who have alloimmunized to HPA-1a*.	Occurrence of neonatal thrombocytopenia and severe neonatal thrombocytopenia
---	--

*For pregnancies that do not result in a live birth, the assessment of alloimmunization will be at 10 weeks from the date of the pregnancy-terminating event (ie, abortion [spontaneous/elective] or stillbirth).

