3.2.2 Alloimmunization Follow-up Population

The Alloimmunization Follow-up Population consists of all participants identified at screening to be at higher risk for HPA-1a alloimmunization (i.e., HPA-1b/b, HLA-DRB3*01:01 positive, anti-HPA-1a antibody negative, carrying an HPA-1a positive fetus), and who have a Week 10 postpartum HPA-1a alloimmunization test result.

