5.3.4 Sensitivity Analyses

No formal sensitivity analysis will be performed.

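### Pregnancy-outcome rates are restricted to higher-risk women with a Week 10 antibody result, which is narrower than the objective and could distort loss rates if testing depends on the outcome

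*SAP*

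**What the plan says.** The protocol objective (Section 3) is "To inform the frequency of pregnancy outcomes among pregnant women identified at higher FNAIT risk". SAP Section 2, Table 1 says the same in its own terms: "To inform the frequency of specific pregnancy outcomes among pregnant women identified to be at higher risk for HPA-1a alloimmunization". Neither adds a condition about a later test.

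SAP 3.2.2 defines the Alloimmunization Follow-up Population as women at higher risk at screening "and who have a Week 10 postpartum HPA-1a alloimmunization test result". SAP 5.3.3.3 then uses that population for all pregnancy-outcome rates, that is, "among pregnant women identified to be at higher risk for HPA-1a alloimmunization and who have a Week 10 postpartum HPA-1a alloimmunization test result".

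Protocol 4.2.3 gives the source of the outcome when there is no live birth: "Pregnancy outcome: spontaneous abortion, elective abortion, stillbirth, including the date (based on medical records". Protocol 4.2.2 also uses medical records for live births. After a loss, "the assessment of alloimmunization will be at 10 weeks from the date of the pregnancy-terminating event".

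SAP 5.3.3.2 provides a separate listing of higher-risk women "for whom a 10 week follow up alloimmunization determination is missing". It shows each woman's pregnancy outcome and the reason for the missing determination. SAP 5.4 counts the higher-risk women and those of them who were assessed at 10 weeks. Missing data are not replaced (SAP 5.6.2), and "No formal sensitivity analysis will be performed" (SAP 5.3.4).

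**The concern.** A secondary endpoint is to be estimated in a subset that its objective does not name, and the SAP gives no reason. The subset is defined by an event that follows the outcome. After a miscarriage, termination or stillbirth, the blood draw falls ten weeks later, and a woman may be less willing to return for it. If so, losses are removed from the rates more often than births are.

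The restriction is also unnecessary, because the outcome does not come from the sample. And it sits badly with protocol 5.4, under which data up to withdrawal of consent are included in the analysis. A woman whose loss is recorded and who withdraws before Week 10 has usable outcome data, yet she enters no rate.

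At stake is whether the reported rates describe higher-risk pregnancies or only those of women who completed the research visit.

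**Working it through.** **Figures in the plan.** The documents state no loss rate, Week 10 return rate or dropout rate, so there is no planned outcome rate to reproduce. The only relevant figure is the 30 to 50 higher-risk women expected from 20,000 to 30,000 enrolled (protocol 4.1.1, SAP 5.8). The frequencies for Caucasian women in protocol Section 2 give 20,000 × 0.02 × 0.27 × 0.85 = 92 and 30,000 × 0.02 × 0.27 × 0.85 = 138. That gap is not called an error here: the 2% is for Caucasian women, and no frequency is given for the mixed population planned. The size of the group is taken as stated.

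**Formula.** Let p be the true share of higher-risk pregnancies ending in loss, rL the share of women with a loss who have a Week 10 result, and rB that share among women with a live birth. The SAP rate estimates

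p·rL / [p·rL + (1 − p)·rB].

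If rL = rB, this equals p. If rL < rB it is below p, and if rL > rB it is above p.

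**Range, all values assumed.** For p = 5%, rL = 0.5, rB = 0.9: 0.025 / (0.025 + 0.855) = 2.8%. For rL = 0.9, rB = 0.7: 0.045 / (0.045 + 0.665) = 6.3%. The same formula gives:

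| True loss share | rL 0.9, rB 0.9 | 0.7, 0.9 | 0.5, 0.9 | 0.3, 0.9 | 0.9, 0.7 |
|---|---|---|---|---|---|
| 5% | 5.0% | 3.9% | 2.8% | 1.7% | 6.3% |
| 10% | 10.0% | 8.0% | 5.8% | 3.6% | 12.5% |
| 15% | 15.0% | 12.1% | 8.9% | 5.6% | 18.5% |

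**In numbers of women (assumed counts, about 90% of women with a live birth tested; exact 95% intervals).**

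- 40 women, 2 losses: all women give 2/40 = 5.0% (0.6 to 16.9). With one loss untested and 34 births tested, 1/35 = 2.9% (0.1 to 14.9).
- 30 women, 3 losses: all women give 3/30 = 10.0% (2.1 to 26.5). With two losses untested and 24 births tested, 1/25 = 4.0% (0.1 to 20.4).
- 50 women, 5 losses: all women give 5/50 = 10.0% (3.3 to 21.8). With 40 births tested, 2 of 5 losses tested gives 2/42 = 4.8% (0.6 to 16.2), and 5 of 5 gives 5/45 = 11.1% (3.7 to 24.1).

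**Choice of the replacement denominator.** Placing women of unknown outcome in the denominator would count them as non-events. With an assumed 50 women, 10 unknown and 4 known losses, that gives 4/50 = 8%, against 4/40 = 10% among known outcomes. Unknowns should therefore be reported but kept out of the denominator.

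**The case against.** It can fairly be said that the women left out do not disappear. The SAP lists them with outcome and reason and counts them in the disposition. In a group this small, a reader could rebuild the full rate wherever the outcome is known. This stands, and it limits the harm. It does not supply the missing analysis: a secondary endpoint should not have to be reassembled from listings.

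A reader might infer that loss rates are biased downward. The documents do not support that as a fact. No section gives a return rate or says that women with losses return less often. Equal testing leaves no bias, and the reverse pattern overstates losses. The intervals above are also wide and overlap heavily, in a descriptive study that tests no hypothesis.

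Two further inferences go too far. One is that the race and ethnicity results are contaminated by retention: SAP 5.3.2 already gives the proportion at each risk step by race, ethnicity and region in the Baseline Screened Population, with no Week 10 condition. The other is that a later treated cohort would look worse. The data are planned as an external control (protocol Section 2, SAP Section 1), but neither document says that loss rates will be the comparator.

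Finally, protocol 4.2.2 and 4.2.3 place outcome collection among the follow-up visit assessments, so some women who miss the visit may also lack an outcome. This too stands, and it is why the fix below is confined to known outcomes.

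**Conclusion.** The concern holds as a mismatch between objective and analysis. SAP 5.3.3.3 estimates pregnancy outcomes in a subset selected after the outcome, while the objective is all higher-risk women, and no planned rate or sensitivity analysis covers the difference. This rests on the text alone.

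Any bias is conditional on testing differing by outcome. For an assumed true loss share of 5%, the reported rate runs from 1.7% to 6.3% over the return rates examined, with no bias when return is equal. In absolute terms the effect is one or two women, which in a group of 30 to 50 is enough to halve the rate roughly. It should be corrected, but it is a fault in a secondary descriptive endpoint and not evidence that loss rates will be too low.

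**What to change.** In SAP 5.3.3.3:

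1. Compute the outcome rates in all women classified at higher risk at screening whose pregnancy outcome is known, whether or not a Week 10 result exists. For women who withdraw, use data up to withdrawal, as protocol 5.4 provides.
2. Report the number with unknown outcome separately, outside the denominator.
3. Keep the Week 10 subset only for the breakdown by alloimmunization status, and add a column for women whose Week 10 result is missing.
4. State that women whose sample is excluded under SAP 5.6.1 (taken before 8 weeks postpartum) stay in the outcome rates. That section removes them only from the antibody analysis and is silent on this.

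Rows under the alloimmunization rate that count untested women as all negative and all positive would be an optional extra; this point does not depend on them.

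The cost is a change of SAP wording and one more table. The SAP already plans to list pregnancy outcome for these women. The outcome may be unobtainable for some who withdrew or were lost, so the corrected rate still assumes that a known outcome is not itself related to the outcome. The separate count of unknowns lets the reader judge that.

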5.3.3.4 Occurrence of Neonatal thrombocytopenia and severe neonatal thrombocytopenia

Outcome of non-severe or severe neonatal thrombocytopenia will be calculated as (type of thrombocytopenia) / (number of neonates for whom a platelet count was available), with attention to Week 10 postpartum alloimmunization status (i.e., alloimmunized vs. not alloimmunized).

Based on the anticipated small numbers of neonates with thrombocytopenia in this study, there will be no further sub-analyses of the data beyond maternal Week 10 postpartum alloimmunization status.

For each neonate with non-severe or severe thrombocytopenia, there will be a listing with the following data elements: Participant ID, region, race, ethnicity, maternal obstetric history, gestational age at birth, and Week 10 postpartum HPA-1a alloimmunization status, and any FNAIT-related interventions during the pregnancy.

[figure not shown]
5.3.4 Sensitivity Analyses

No formal sensitivity analysis will be performed.

5.4 Study Participants

The alloimmunization study populations are characterized in the flowchart (Figure 2). Consented participants are those that have provided informed consent for the study. Eligible participants are those that meet protocol inclusion and exclusion criteria.

Figure 2 Flowchart of Participant Disposition

A clear accounting of the disposition of all participants who enter the study will be provided, from initial consent to study completion. This will include the numbers of the following groups:

- Number of participants consented
- Number of eligible participants
- Number of participants confirmed HPA-1b/b (vs. HPA-1aa or HPA-1a/b)
- Number of HPA-1b/b participants confirmed HLA-DRB3*01:01 positive (vs. negative)
- Number of HPA-1b/b and HLA-DRB3*01:01 positive participants who are HPA-1a alloantibody negative (vs. positive)
- Number of HPA-1b/b and HLA-DRB3*01:01 positive participants who are HPA-1a alloantibody negative and who have an HPA-1a positive fetus (vs. HPA-1b/b fetus)
- Number of HPA-1b/b and HLA-DRB3*01:01 positive participants who are HPA-1a alloantibody negative and have an HPA-1a positive fetus and who are assessed for presence of HPA-1a alloantibodies at 10 weeks postpartum
- Number of participants missing expected FNAIT Laboratory results as described by the testing sequence and their prior test result(s)

